9.5.4. Laboratory Evaluations

Summaries of clinical laboratory data will be provided using descriptive statistics. No inferential statistics will be provided. Quantitative values and change from baseline in quantitative values will be summarized by dose group. Listings of all laboratory results and reference ranges will be provided.

Graded laboratory abnormalities will be defined using the grading scheme based on CTCAE (4.03). The incidence of treatment-emergent laboratory abnormalities, defined as values that increase at least one toxicity grade from baseline at any time post baseline up to and including the date of last dose of study drug, will be summarized by treatment group. If baseline data are missing, then any graded abnormality (i.e., at least a Grade 1) will be considered treatment emergent.

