Median	XX.X	XX.X	XX.X	XX.X	XX.X	XX.X	XX.X
Maximum	XX	XX	XX	XX	XX	XX	XX
Cycle 1-Day 4							
n	XX	XX	XX	XX	XX	XX	XX
Mean	XX.X	XX.X	XX.X	XX.X	XX.X	XX.X	XX.X
SD	XX.XX	XX.XX	XX.XX	XX.XX	XX.XX	XX.XX	XX.XX
Minimum	XX	XX	XX	XX	XX	XX	XX
Median	XX.X	XX.X	XX.X	XX.X	XX.X	XX.X	XX.X
Maximum	XX	XX	XX	XX	XX	XX	XX
Change from Baseline to Cycle 1-Day 4							
n	XX	XX	XX	XX	XX	XX	XX
Mean	XX.X	XX.X	XX.X	XX.X	XX.X	XX.X	XX.X
SD	XX.XX	XX.XX	XX.XX	XX.XX	XX.XX	XX.XX	XX.XX
Minimum	XX	XX	XX	XX	XX	XX	XX
Median	XX.X	XX.X	XX.X	XX.X	XX.X	XX.X	XX.X
Maximum	XX	XX	XX	XX	XX	XX	XX

<repeat for Cycle 1 Day 10 visit>
<for Cycle 2 to last-1 Cycle, repeat for Day 1 visit and Day 4 visit>
<for the last Cycle, repeat for Day 22 visit and Day 28 follow-up visit>

[a] Baseline was the last value/result of assessment prior to or on day of first study treatment.

Program: (Program name.sas) (run on: DDMMYYYY HH:MM)

Filename: (Specify file name.rtf)

PROGRAMMING NOTES:

- Repeat for all hematology parameters: Hemoglobin, Hematocrit, Platelet count, RBC count, Reticulocytes, WBC Count with Differential, Neutrophils, Lymphocytes, Monocytes, Eosinophils, Basophils.

Protocol: CPX-POM-001

--- DELIVERY TYPE ----

Page 1 of X

Table 14.3-2.1.2 - Outside of Normal Range - Shift Table for Hematology Laboratory Parameters
 (Safety Population)

Dose group : CPX-POM 30 mg/m² (N=1)

Parameter/ Visit	Value at Visit	Baseline [a] value				Total
		Low n (%)	Normal n (%)	High n (%)	Low/High* n (%)	
Hemoglobin (unit)						
Cycle 1-Day 4 (N**=XX)	Low	XX (XXX.X)	XX (XXX.X)	XX (XXX.X)	XX (XXX.X)	XX (XXX.X)
	Normal	XX (XXX.X)	XX (XXX.X)	XX (XXX.X)	XX (XXX.X)	XX (XXX.X)
	High	XX (XXX.X)	XX (XXX.X)	XX (XXX.X)	XX (XXX.X)	XX (XXX.X)
	Low/High*	XX (XXX.X)	XX (XXX.X)	XX (XXX.X)	XX (XXX.X)	XX (XXX.X)
	Total	XX (XXX.X)	XX (XXX.X)	XX (XXX.X)	XX (XXX.X)	XX
Cycle 1-Day 10 (N**=XX)	Low	XX (XXX.X)	XX (XXX.X)	XX (XXX.X)	XX (XXX.X)	XX (XXX.X)
	Normal	XX (XXX.X)	XX (XXX.X)	XX (XXX.X)	XX (XXX.X)	XX (XXX.X)
	High	XX (XXX.X)	XX (XXX.X)	XX (XXX.X)	XX (XXX.X)	XX (XXX.X)
	Low/High*	XX (XXX.X)	XX (XXX.X)	XX (XXX.X)	XX (XXX.X)	XX (XXX.X)
	Total	XX (XXX.X)	XX (XXX.X)	XX (XXX.X)	XX (XXX.X)	XX

<for Cycle 2 to last-1 Cycle, repeat for Day 1 visit and Day 4 visit>
 <for the last Cycle, repeat for Day 22 visit and Day 28 follow-up visit>
 <repeat for all doses groups>

Percentage was based on the number of patients present at each visit with non-missing results for the considered parameter.

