* Included patients with Low or High results. ** Denominator of the percentage.

[a] Baseline was the last value/result of assessment prior to or on day of first study treatment intake.

Program: (Program name.sas) (run on: DDMMYYYY HH:MM)

Filename: (Specify file name.rtf)

PROGRAMMING NOTES:

- Repeat for all doses groups.

Sponsor: CicloMed
Protocol: CPX-POM-001
Statistical Analysis Plan
(TFL shells):
Version 1.0 / 02FEB2018

- Repeat for all hematology parameters: Hemoglobin, Hematocrit, Platelet count, RBC count, Reticulocytes, WBC Count with Differential, Neutrophils, Lymphocytes, Monocytes, Eosinophils, Basophils.

Table 14.3-2.1.3 - Clinician Assessment - Shift Table for Hematology Laboratory Parameters
 (Safety Population)

Dose group : CPX-POM 30 mg/m² (N=1)

Parameter/ Visit	Value at Visit	Baseline [a] value			Total
		Normal n (%)	Abnormal, NCS n (%)	Abnormal, CS n (%)	
Hemoglobin (unit)					
Cycle 1-Day 4 (N*=XX)	Normal	XX (XXX.X)	XX (XXX.X)	XX (XXX.X)	XX (XXX.X)
	Abnormal, NCS	XX (XXX.X)	XX (XXX.X)	XX (XXX.X)	XX (XXX.X)
	Abnormal, CS	XX (XXX.X)	XX (XXX.X)	XX (XXX.X)	XX (XXX.X)
	Total	XX (XXX.X)	XX (XXX.X)	XX (XXX.X)	XX
Cycle 1-Day 10 (N*=XX)	Normal	XX (XXX.X)	XX (XXX.X)	XX (XXX.X)	XX (XXX.X)
	Abnormal, NCS	XX (XXX.X)	XX (XXX.X)	XX (XXX.X)	XX (XXX.X)
	Abnormal, CS	XX (XXX.X)	XX (XXX.X)	XX (XXX.X)	XX (XXX.X)
	Total	XX (XXX.X)	XX (XXX.X)	XX (XXX.X)	XX

<for Cycle 2 to last-1 Cycle, repeat for Day 1 visit and Day 4 visit>
 <for the last Cycle, repeat for Day 22 visit and Day 28 follow-up visit>
 <repeat for the other hematology parameters>
 <repeat for all doses groups>

Percentage was based on the number of patients present at each visit with non-missing results for the considered parameter.

* Denominator of the percentage.

[a] Baseline was the last value/result of assessment prior to or on day of first study treatment.

CS = Clinically Significant; NCS = Not Clinically Significant.

Program: (Program name.sas) (run on: DDMMYYYY HH:MM)

Filename: (Specify file name.rtf)

PROGRAMMING NOTES:

- Repeat for all doses groups.
- Repeat for all hematology parameters: Hemoglobin, Hematocrit, Platelet count, RBC count, Reticulocytes, WBC Count with Differential, Neutrophils, Lymphocytes, Monocytes, Eosinophils, Basophils.

Table 14.3-2.1.4 - On-study Hematology Adverse Events: Worst NCI-CTCAE Grade per patient
(Safety Population)

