Parameter/ Worst NCI-CTCAE grade	CPX-POM 30 mg/m ² N=1 n (%)	CPX-POM [D2] mg/m ² N=X n (%)	CPX-POM [D3] mg/m ² N=X n (%)	CPX-POM [D4] mg/m ² N=X n (%)	CPX-POM [D5] mg/m ² N=X n (%)	CPX-POM [D6] mg/m ² N=X n (%)	CPX-POM [D7] mg/m ² N=X n (%)
Hemoglobin (unit)							
Normal	XX (XX.X)	XX (XX.X)	XX (XX.X)	XX (XX.X)	XX (XX.X)	XX (XX.X)	XX (XX.X)
Grade 1	XX (XX.X)	XX (XX.X)	XX (XX.X)	XX (XX.X)	XX (XX.X)	XX (XX.X)	XX (XX.X)
Grade 2	XX (XX.X)	XX (XX.X)	XX (XX.X)	XX (XX.X)	XX (XX.X)	XX (XX.X)	XX (XX.X)
Grade 3	XX (XX.X)	XX (XX.X)	XX (XX.X)	XX (XX.X)	XX (XX.X)	XX (XX.X)	XX (XX.X)
Grade 4	XX (XX.X)	XX (XX.X)	XX (XX.X)	XX (XX.X)	XX (XX.X)	XX (XX.X)	XX (XX.X)
Missing	XX (XX.X)	XX (XX.X)	XX (XX.X)	XX (XX.X)	XX (XX.X)	XX (XX.X)	XX (XX.X)
Hematocrit (unit)							
Normal	XX (XX.X)	XX (XX.X)	XX (XX.X)	XX (XX.X)	XX (XX.X)	XX (XX.X)	XX (XX.X)
Grade 1	XX (XX.X)	XX (XX.X)	XX (XX.X)	XX (XX.X)	XX (XX.X)	XX (XX.X)	XX (XX.X)
Grade 2	XX (XX.X)	XX (XX.X)	XX (XX.X)	XX (XX.X)	XX (XX.X)	XX (XX.X)	XX (XX.X)
Grade 3	XX (XX.X)	XX (XX.X)	XX (XX.X)	XX (XX.X)	XX (XX.X)	XX (XX.X)	XX (XX.X)
Grade 4	XX (XX.X)	XX (XX.X)	XX (XX.X)	XX (XX.X)	XX (XX.X)	XX (XX.X)	XX (XX.X)
Missing	XX (XX.X)	XX (XX.X)	XX (XX.X)	XX (XX.X)	XX (XX.X)	XX (XX.X)	XX (XX.X)

<repeat for the other hematology parameters>

For a given laboratory parameter, a patient must have at least one on-study grade assessed to be included.
For a given laboratory parameter, the number of treated patients with at least one on-study grade assessed for that parameter will be used as the denominator for the calculation of percentages.
A patient with multiple results for a parameter will only be counted under the maximum NCI-CTCAE grade for this parameter.
Laboratory ranges are based on NCI-CTCAE version 4.0.

Program: (Program name.sas) (run on: DDMMYYYY HH:MM)

Filename: (Specify file name.rtf)

PROGRAMMING NOTES:

- Repeat for all hematology parameters: Hemoglobin, Hematocrit, Platelet count, RBC count, Reticulocytes, WBC Count with

Sponsor: CicloMed
Protocol: CPX-POM-001
Statistical Analysis Plan
(TFL shells):
Version 1.0 / 02FEB2018

Differential, Neutrophils, Lymphocytes, Monocytes, Eosinophils, Basophils.

Table 14.3-2.1.5 - Shift table of Worst NCI-CTCAE Grade for Hematological parameters
(Safety Population)

Parameter	Baseline grade	Worst NCI-CTCAE grade						Total n (%)
		Normal n (%)	Grade 1 n (%)	Grade 2 n (%)	Grade 3 n (%)	Grade 4 n (%)	Missing n (%)	

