Clinical Chemistry parameters are: Potassium, Sodium, Chloride, Glucose, BUN, Creatinine, Creatinine clearance, ALP, ALT, AST, GGT, Alkaline phosphatase, Direct bilirubin, Indirect bilirubin, Total bilirubin, Total protein, Albumin, Calcium, Bicarbonate, Magnesium, Phosphate, Lipase, Amylase

Table 14.3-2.2.2 - Outside of Normal Range - Shift Table for Clinical Chemistry Laboratory Parameters
(Safety Population)

Replicate of Table 14.3-2.1.2

PROGRAMMING NOTES:

Clinical Chemistry parameters are: Potassium, Sodium, Chloride, Glucose, BUN, Creatinine, Creatinine clearance, ALP, ALT, AST, GGT, Alkaline phosphatase, Direct bilirubin, Indirect bilirubin, Total bilirubin, Total protein, Albumin, Calcium, Bicarbonate, Magnesium, Phosphate, Lipase, Amylase

Table 14.3-2.2.3 - Clinician Assessment - Shift Table for Clinical Chemistry Laboratory Parameters
(Safety Population)

Replicate of Table 14.3-2.1.3

PROGRAMMING NOTES:

Clinical Chemistry parameters are: Potassium, Sodium, Chloride, Glucose, BUN, Creatinine, Creatinine clearance, ALP, ALT, AST, GGT, Alkaline phosphatase, Direct bilirubin, Indirect bilirubin, Total bilirubin, Total protein, Albumin, Calcium, Bicarbonate, Magnesium, Phosphate, Lipase, Amylase

Table 14.3-2.2.4 - On-study Clinical Chemistry Adverse Events: Worst NCI-CTCAE Grade per patient
(Safety Population)

Replicate of Table 14.3-2.1.4

PROGRAMMING NOTES:

Clinical Chemistry parameters are: Potassium, Sodium, Chloride, Glucose, BUN, Creatinine, Creatinine clearance, ALP, ALT, AST,

Sponsor: CicloMed
Protocol: CPX-POM-001
Statistical Analysis Plan
(TFL shells):
Version 1.0 / 02FEB2018

GGT, Alkaline phosphatase, Direct bilirubin, Indirect bilirubin, Total bilirubin, Total protein, Albumin, Calcium, Bicarbonate, Magnesium, Phosphate, Lipase, Amylase

Table 14.3-2.2.5 - Shift table of Worst NCI-CTCAE Grade for Clinical Chemistry Laboratory parameters
(Safety Population)

Replicate of Table 14.3-2.1.5

PROGRAMMING NOTES:

Clinical Chemistry parameters are: Potassium, Sodium, Chloride, Glucose, BUN, Creatinine, Creatinine clearance, ALP, ALT, AST, GGT, Alkaline phosphatase, Direct bilirubin, Indirect bilirubin, Total bilirubin, Total protein, Albumin, Calcium, Bicarbonate, Magnesium, Phosphate, Lipase, Amylase

Table 14.3-2.3.1 - Summary of Coagulation Laboratory Data
(Safety Population)

Replicate of Table 14.3-2.1.1

PROGRAMMING NOTES:

- Coagulation parameters are PT and aPTT.
- Only Day 1 visit of each cycle

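### The CTCAE worst-grade and shift tables do not separate low from high, so graded rows carry no direction and some new opposite-direction abnormalities do not count as treatment-emergent

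*SAP*

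**What the plan says.** SAP Table 14.3-2.1.4 reports the worst on-study CTCAE grade per patient. Each hematology parameter has one block of rows: Normal, Grades 1 to 4, Missing. Its footnote states that "A patient with multiple results for a parameter will only be counted under the maximum NCI-CTCAE grade for this parameter".

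The next shell, "Table 14.3-2.1.5 - Shift table of Worst NCI-CTCAE Grade for Hematological parameters", crosses baseline grade with worst grade on the same single scale and repeats that footnote.

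Both layouts pass unchanged to chemistry: Table 14.3-2.2.4 is given as "Replicate of Table 14.3-2.1.4" and Table 14.3-2.2.5 as "Replicate of Table 14.3-2.1.5". The programming note names each analyte once: "Clinical Chemistry parameters are: Potassium, Sodium, Chloride, Glucose, BUN, Creatinine, Creatinine clearance", and so on through calcium, magnesium and the rest.

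Protocol 9.5.4 defines treatment-emergent laboratory abnormalities as "values that increase at least one toxicity grade from baseline at any time post baseline", up to the last dose date. It says nothing about direction.

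Direction does appear in "Table 14.3-2.1.2 - Outside of Normal Range - Shift Table for Hematology Laboratory Parameters", which has separate Low, Normal and High categories at baseline and at each visit, plus a combined category footnoted "Included patients with Low or High results". Table 14.3-2.2.2 replicates it for chemistry. Neither of these tables carries a CTCAE grade.

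**The concern.** A low and a high value of the same analyte are different findings. The plan recognizes this elsewhere: the normal-range shift tables separate the two, and Protocol 5.2 lists hypokalemia among the torsade risk factors that exclude a patient. Yet a row reading potassium, Grade 2 does not say whether potassium was low or high.

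Two things are at stake in the safety summaries. First, grade and direction never appear together in a summary table, and a patient with events on both sides keeps only the higher grade. Second, a patient who enters abnormal on one side and becomes newly abnormal on the other may show no grade increase. That patient then drops out of the treatment-emergent incidence that 9.5.4 promises by treatment group.

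**Working it through.** No figure in the documents depends on this rule, so there is none to reproduce. The check scores every possible case under the rule as written, then again with direction kept.

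**Inputs.** The maximum-grade footnote and single scale (SAP Tables 14.3-2.1.4 and 14.3-2.1.5 and their chemistry replicates); the increase of at least one grade (Protocol 9.5.4). Assumption: the analyte can be graded on both sides. The CTCAE grading tables are not reproduced in the documents.

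**Set-up.** Let b be the baseline grade (1 to 4) in one direction. Let w be the worst on-treatment grade (1 to 4) in the opposite direction, with nothing abnormal on treatment in the baseline direction. This gives 4 × 4 = 16 pairs.

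**As written.** The shift table reads Grade b to Grade w, and 9.5.4 requires w − b ≥ 1.

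| Case | Pairs | How it reads | Meets 9.5.4? |
|---|---|---|---|
| w = b | 4 | No shift | No |
| w < b | 3 + 2 + 1 = 6 | Improvement | No |
| w > b | 3 + 2 + 1 = 6 | Worsening, direction unlabelled | Yes |

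Pairs not counted as treatment-emergent: 4 + 6 = 10 of 16.

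**With direction kept.** In the new direction the baseline is Normal (Grade 0), so the increase is w − 0 ≥ 1 for every pair. All 16 of 16 count, and the resolution on the old side shows separately as Grade b to Normal.

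**Worked records.**

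| Baseline | On treatment | As written | Low row | High row |
|---|---|---|---|---|
| Low G2 | High G2 | G2 to G2 | G2 to Normal | Normal to G2 |
| Low G2 | High G3 | G2 to G3 | G2 to Normal | Normal to G3 |
| Low G3 | High G1 | G3 to G1 | G3 to Normal | Normal to G1 |
| Low G2 | Low G2, High G1 | G2 to G2 | G2 to G2 | Normal to G1 |
| Normal | Low G2, High G3 | Normal to G3 | Normal to G2 | Normal to G3 |

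The fourth record shows that the old abnormality need not resolve for the new one to be hidden. The fifth shows a loss that does not depend on the baseline: in the worst-grade tables (14.3-2.1.4 and 14.3-2.2.4) the Grade 2 low event is absorbed into an unlabelled Grade 3.

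**Leverage of one patient.** The escalation cohorts in Protocol Table 2 have 1 to 6 patients. If one patient is misclassified and all in the group are evaluable, that group's incidence changes by 1/6 = 16.7 to 1/1 = 100 percentage points.

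**The case against.** The strongest reply is that direction is reported elsewhere. Tables 14.3-2.1.2 and 14.3-2.2.2 would show a high-to-low swing by visit and dose group. Tables 14.3-2.1.1 and 14.3-2.2.1 give signed changes from baseline. Listing 16.2.8-1 and its chemistry replicate 16.2.8-2 put result, L/H flag and grade on one line per record. Protocol 8.2.3.6 also sends clinically significant abnormal results to the adverse event form. With about 24 escalation patients, a reader can recover every case from the listings. All of this stands, and it limits the harm. It does not supply the missing summary: the range tables have no grade, the graded tables have no direction, adverse event capture depends on an opinion of clinical significance, and a listing does not correct the 9.5.4 incidence.

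A second reply is that 9.5.4 is merely silent on direction and that the supplied SAP is a set of shells. The footnote to Listing 16.2.8-5 points to SAP text, where a direction rule might sit. That cannot be excluded, but no such rule appears in the documents supplied. Applied to the single grade in the shells, 9.5.4 gives the result shown.

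Three stronger readings are tempting and are not supported.

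- A reader might infer that any swing from low to high is recorded as no shift. That holds only for equal grades. It also concerns the shift tables alone, since Table 14.3-2.1.4 has no baseline axis.
- A reader might infer from Protocol Section 2, which describes ciclopirox as a metal chelator, that the direction of calcium or magnesium is a prime safety question. That section gives iron and aluminum as its examples and reports no clinical chemistry changes in the 28-day rat and dog studies.
- A reader might want an expected number of missed events. The documents give no rates of two-sided abnormality from which to derive one.

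**Conclusion.** The point holds for the graded summary tables and for the treatment-emergent rule. For two-sided analytes, every graded row lacks direction, and an event of lower grade on the other side is lost. A new abnormality opposite to the baseline one goes uncounted as treatment-emergent in 10 of 16 kinds of grade pair; in the other 6 it appears as a worsening with no direction. These counts describe possible pairs, not how often they occur, and the number of patients affected cannot be derived from the documents.

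The conclusion rests on two assumptions: that the named analytes are graded separately on the low and high sides, and that no direction rule exists in SAP text outside the shells. The effect is confined to descriptive safety summaries. DLT assessment, dose escalation, the MTD and the sample size do not use these tables. The change is worth making because it is cheap and because the dose groups are small, but no primary conclusion of the trial depends on it.

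**What to change.** In Protocol 9.5.4 and in SAP Tables 14.3-2.1.4, 14.3-2.1.5, 14.3-2.2.4 and 14.3-2.2.5:

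1. List the analytes graded in both directions and give each a low row and a high row.
2. Within a row, set any baseline or on-treatment value not abnormal in that direction to Grade 0 (Normal). Keep missing results as Missing.
3. Take the baseline grade, the maximum on-treatment grade and treatment-emergence within direction, and amend the maximum-grade footnote to say so.
4. If SAP text outside the shells already contains such a rule, carry it into the shells.

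The cost is a few extra table rows and some footnote wording. The result, normal range, L/H flag and grade are already planned for each record in the laboratory listings, so no new data are needed. Protocol Section 9 has the analysis plan finalized before database lock, which is the time to make the change.

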9.5.3. Adverse Events

Clinical and laboratory AEs will be coded using the Medical Dictionary for Regulatory Activities (MedDRA). System Organ Class (SOC), High-Level Group Term (HLGT), High-Level Term (HLT), Preferred Term, and Lower-Level Term (LLT) will be attached to the clinical database.

AEs will be summarized on the basis of the date of onset for the event. A treatment-emergent AE will be defined as any AE that begins on or after the date of first dose of CPX-POM.

Summaries (number and percentage of patients) of treatment-emergent AEs (by SOC, and Preferred Term) will be provided by dose group and overall:

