Preferred Term #1	XX (XX.X)	XX (XX.X)	XX (XX.X)	XX (XX.X)	XX (XX.X)	XX (XX.X)	XX (XX.X)
Preferred Term #2	XX (XX.X)	XX (XX.X)	XX (XX.X)	XX (XX.X)	XX (XX.X)	XX (XX.X)	XX (XX.X)
Preferred Term #3	XX (XX.X)	XX (XX.X)	XX (XX.X)	XX (XX.X)	XX (XX.X)	XX (XX.X)	XX (XX.X)
<etc>							

If there was more than one TEAE reported under the same System Organ Class and Preferred Term, the patient was counted only once under that System Organ Class and that Preferred Term. If there was more than one TEAE reported under the same System Organ Class, the patient was counted only once under that System Organ Class.
 MedDRA version <version number>.

Program: (Program name.sas) (run on: DDMMYYYY HH:MM)

Filename: (Specify file name.rtf)

PROGRAMMING NOTES:

- The System Organ Classes are presented by decreasing frequency (within the total column - all CPX-POM doses groups combined - not displayed) and the Preferred Terms within a System Organ Class are presented by decreasing frequency (within the total column - all CPX-POM doses groups combined - not displayed).

Sponsor: CicloMed
Protocol: CPX-POM-001
Statistical Analysis Plan
(TFL shells):
Version 1.0 / 02FEB2018

Table 14.3-1.3 - Number (%) of Patients with Related Treatment-Emergent Adverse Events by System Organ Class and Preferred Term
(Safety Population)

Replicate of Table 14.3-1.2

Table 14.3-1.4 - Number (%) of Patients with Serious Treatment-Emergent Adverse Events by System Organ Class and Preferred Term
(Safety Population)

Replicate of Table 14.3-1.2

Table 14.3-1.5 - Number (%) of Patients with Serious Related Treatment-Emergent Adverse Events by System Organ Class and
Preferred Term
(Safety Population)

Replicate of Table 14.3-1.2

Table 14.3-1.6 - Number (%) of Patients with Treatment-Emergent Adverse Events Leading to Discontinuation by System Organ Class
and Preferred Term
(Safety Population)

Replicate of Table 14.3-1.2

PROGRAMMING NOTES:

- "Leading to discontinuation" is derived from action taken = permanently discontinued.

Table 14.3-1.7 - Number (%) of Patients with Treatment-Emergent Adverse Events
 by System Organ Class, Preferred Term and Maximal Severity
 (Safety Population)

System Organ Class/ Preferred Term/ Maximal severity	CPX-POM 30 mg/m ² N=1 n (%)	CPX-POM [D2] mg/m ² N=X n (%)	CPX-POM [D3] mg/m ² N=X n (%)	CPX-POM [D4] mg/m ² N=X n (%)	CPX-POM [D5] mg/m ² N=X n (%)	CPX-POM [D6] mg/m ² N=X n (%)	CPX-POM [D7] mg/m ² N=X n (%)
Number of patients with any TEAE							

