Hematocrit (unit)	Normal	XX (XXX.X)	XX (XXX.X)	XX (XXX.X)	XX (XXX.X)	XX (XXX.X)	XX (XXX.X)	XX (XXX.X)
	Grade 1	XX (XXX.X)	XX (XXX.X)	XX (XXX.X)	XX (XXX.X)	XX (XXX.X)	XX (XXX.X)	XX (XXX.X)
	Grade 2	XX (XXX.X)	XX (XXX.X)	XX (XXX.X)	XX (XXX.X)	XX (XXX.X)	XX (XXX.X)	XX (XXX.X)
	Grade 3	XX (XXX.X)	XX (XXX.X)	XX (XXX.X)	XX (XXX.X)	XX (XXX.X)	XX (XXX.X)	XX (XXX.X)
	Grade 4	XX (XXX.X)	XX (XXX.X)	XX (XXX.X)	XX (XXX.X)	XX (XXX.X)	XX (XXX.X)	XX (XXX.X)
	Missing	XX (XXX.X)	XX (XXX.X)	XX (XXX.X)	XX (XXX.X)	XX (XXX.X)	XX (XXX.X)	XX (XXX.X)
	Total	XX (XXX.X)	XX (XXX.X)	XX (XXX.X)	XX (XXX.X)	XX (XXX.X)	XX (XXX.X)	XX (XXX.X)
Hemoglobin (unit)	Normal	XX (XXX.X)	XX (XXX.X)	XX (XXX.X)	XX (XXX.X)	XX (XXX.X)	XX (XXX.X)	XX (XXX.X)
	Grade 1	XX (XXX.X)	XX (XXX.X)	XX (XXX.X)	XX (XXX.X)	XX (XXX.X)	XX (XXX.X)	XX (XXX.X)
	Grade 2	XX (XXX.X)	XX (XXX.X)	XX (XXX.X)	XX (XXX.X)	XX (XXX.X)	XX (XXX.X)	XX (XXX.X)
	Grade 3	XX (XXX.X)	XX (XXX.X)	XX (XXX.X)	XX (XXX.X)	XX (XXX.X)	XX (XXX.X)	XX (XXX.X)
	Grade 4	XX (XXX.X)	XX (XXX.X)	XX (XXX.X)	XX (XXX.X)	XX (XXX.X)	XX (XXX.X)	XX (XXX.X)
	Missing	XX (XXX.X)	XX (XXX.X)	XX (XXX.X)	XX (XXX.X)	XX (XXX.X)	XX (XXX.X)	XX (XXX.X)
	Total	XX (XXX.X)	XX (XXX.X)	XX (XXX.X)	XX (XXX.X)	XX (XXX.X)	XX (XXX.X)	XX (XXX.X)

<repeat for the other hematology parameters>

For a given laboratory parameter, a patient must have at least one baseline and one on-treatment grades assessed to be included. For a given laboratory parameter, the number of treated patients with at least one baseline and one on-treatment grades assessed for that parameter will be used as the denominator for the calculation of percentages. A patient with multiple results for a parameter will only be counted under the maximum NCI-CTCAE grade for this parameter. Laboratory ranges are based on NCI-CTCAE version 4.0.

Program: (Program name.sas) (run on: DDMMYYYY HH:MM)

Filename: (Specify file name.rtf)

PROGRAMMING NOTES:

- Repeat for all hematology parameters: Hemoglobin, Hematocrit, Platelet count, RBC count, Reticulocytes, WBC Count with Differential, Neutrophils, Lymphocytes, Monocytes, Eosinophils, Basophils.

Sponsor: CicloMed
Protocol: CPX-POM-001
Statistical Analysis Plan
(TFL shells):
Version 1.0 / 02FEB2018

Table 14.3-2.2.1 - Summary of Clinical Chemistry Laboratory Data
(Safety Population)

Replicate of Table 14.3-2.1.1

PROGRAMMING NOTES:

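### No supplied SAP shell gives treatment-emergent laboratory abnormalities by dose, as Protocol 9.5.4 requires; separately, seven adverse-event tables omit the overall column promised in 9.5.3

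*SAP*

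**What the plan says.** **Laboratory data, Protocol 9.5.4.** Treatment-emergent laboratory abnormalities are "defined as values that increase at least one toxicity grade from baseline at any time post baseline", and the sentence continues "up to and including the date of last dose of study drug, will be summarized by treatment group". For absent baselines it adds: "If baseline data are missing, then any graded abnormality (i.e., at least a Grade 1) will be considered treatment emergent".

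**Laboratory data, SAP shells.** Table 14.3-2.1.5 is titled "Shift table of Worst NCI-CTCAE Grade for Hematological parameters". Its rows are baseline grades and its columns are worst grades. It has no dose columns and no dose header, and its programming note repeats it by parameter only. Its footnote states that "a patient must have at least one baseline and one on-treatment grades assessed to be included", and the same group forms the denominator. The body nevertheless prints a baseline row labelled Missing. Tables 14.3-2.2.5 (chemistry) and 14.3-2.5.5 (urinalysis) replicate it without adding a dose instruction.

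**Adverse events.** Protocol 9.5.3 says that summaries of treatment-emergent events by system organ class and preferred term "will be provided by dose group and overall". The notes to SAP Tables 14.3-1.2 and 14.3-1.7 sort rows by frequency "within the total column - all CPX-POM doses groups combined - not displayed". Tables 14.3-1.3 to 14.3-1.6 replicate the first of these, and 14.3-1.8 replicates the second.

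**The concern.** In a dose-escalation trial, the summary laboratory question is how many patients at each dose worsened from where they started. Eligibility admits patients who start with abnormal values: hemoglobin from 9.0 g/dL (inclusion criterion 10), and AST/ALT up to 5 times the upper limit of normal when the liver is involved (criterion 9). A by-dose table that ignores baseline will count such a patient as having an on-study graded abnormality even if nothing changed. A table that respects baseline but pools the doses cannot show which dose the worsening belongs to. A programmer who follows these shells would deliver both tables and still not deliver the incidence that 9.5.4 asks for.

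The adverse-event point is separate. Section 9.5.3 promises an overall figure, and most of the tables compute it for sorting and then leave it out.

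**Working it through.** The plan has no figure to reproduce here, so the check sets the protocol requirement against each laboratory shell. I read *treatment group* in 9.5.4 as dose group, because the trial has one drug and the same section uses dose group for the quantitative summaries.

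**1. Which shell could supply the 9.5.4 incidence?**

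| SAP table (hematology; chemistry and urinalysis replicate it) | By dose | Uses baseline | Measure | Gives grade rise by dose |
|---|---|---|---|---|
| 14.3-2.1.1 | yes | yes | values and change | no |
| 14.3-2.1.2 | yes | yes | normal range, visit by visit | no |
| 14.3-2.1.3 | yes | yes | clinician assessment, visit by visit | no |
| 14.3-2.1.4 | yes | no | worst CTCAE grade | no |
| 14.3-2.1.5 | no | yes | worst CTCAE grade | no |

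Coagulation (14.3-2.3.1) and thyroid (14.3-2.4) have only the descriptive summary. The list of tables has no treatment-emergent laboratory table. Tables 14.3-2.1.2 and 14.3-2.1.3 carry a dose header and an instruction to repeat for every dose group, so the missing dose split in 14.3-2.1.5 stands out within its own series. It is an omission, not an instruction to pool.

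**2. Can Tables 14.3-2.1.4 and 14.3-2.1.5 be combined?** For dose *d*, let k(d) be the number of patients with worst grade 1 or higher, and e(d) the number with a rise of at least one grade. Among patients with a known baseline, Table 14.3-2.1.4 gives only 0 ≤ e(d) ≤ k(d). Table 14.3-2.1.5 gives the sum of e(d) over doses, further broken down by grade. With seven dose columns in the shells, e(d) is not determined in general. It is determined in special cases, for example when every patient with a given worst grade started at normal.

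**3. Missing baseline.** Take a patient with no baseline grade and a later value of Grade 1 or higher. Section 9.5.4 counts that patient as emergent; the footnote of 14.3-2.1.5 removes the patient from numerator and denominator. Suppose the table were split by dose but the footnote kept. With one such patient, no other event, and the whole cohort as the 9.5.4 denominator, a standard cohort of 3 to 6 gives 1/3 = 33.3% to 1/6 = 16.7% under 9.5.4, and 0/2 to 0/5 = 0% under the footnote. The footnote also guarantees that the table's Missing baseline row is empty.

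**4. Time window.** Section 9.5.4 stops at the last dose. The footnote of 14.3-2.1.5 speaks of on-treatment grades and that of 14.3-2.1.4 of on-study grades; the shells define neither. Dosing is on Days 1 to 5. In the Schedule of Assessments, a patient treated for one cycle has post-baseline hematology and chemistry on Day 4, Day 10, Day 22 and at Follow-up. Only Day 4, one of four, falls on or before the last dose. For patients with further cycles, Cycle 1 Day 10 falls inside the window. The reading chosen therefore changes what is counted.

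**5. Adverse-event tables.** Of the nine tables 14.3-1.1 to 14.3-1.9, two (14.3-1.1 and 14.3-1.9) state that an All Doses column is displayed. The other seven rely on a total that is not displayed. If each patient is counted in one dose column, the overall rate is the sum of the displayed n divided by the sum of the displayed N, so a reader can recover it.

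**The case against.** The strongest reply is that little information is lost:

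- Table 14.3-2.1.4 shows worst grade by dose, so a cluster of high-grade values at one dose would be visible.
- Listing 16.2.8-1 and its replicates give the CTCAE grade for each patient at baseline and each visit, within dose group, for roughly 24 escalation patients.
- Clinically significant laboratory abnormalities are also recorded as adverse events (Protocol 8.2.3.6), so they enter the by-dose event tables.
- A shift table needs a baseline by its nature. Missing baselines should be few: hematology and chemistry are drawn at Screening and Day 1, and eligibility requires hemoglobin, platelets, ANC, bilirubin and AST/ALT.
- The file supplied is the table-shell part of the SAP and refers to SAP text that is not included.

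Most of this stands and limits the point. It does not remove it. Section 9.5.4 asks for a summary, and a listing leaves the reader to build one. The adverse-event route depends on a judgement of clinical significance, whereas 9.5.4 depends on grade alone. The need for a baseline would excuse the footnote if another table applied the missing-baseline rule, but no supplied shell does.

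A reader might infer more than the documents support:

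- That the missing adverse-event column causes the laboratory gap. It cannot; these are departures from two different sections.
- That every adverse-event table lacks the overall column. Tables 14.3-1.1 and 14.3-1.9 display it.
- That an adverse event could go unseen without the column. Any event counted overall also appears in some dose column.
- That the shells hide laboratory toxicity by dose altogether. Table 14.3-2.1.4 shows it, without separating what was present at baseline.

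**Conclusion.** Two separate departures from the protocol hold for the supplied shells. The main one is that no shell summarizes treatment-emergent laboratory abnormalities by dose, across the hematology, chemistry and urinalysis panels. The grade-shift tables lack a dose split, and their footnote conflicts both with the missing-baseline rule of 9.5.4 and with their own Missing row. The dose split matters more than the footnote.

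The minor one is that seven of the nine adverse-event tables omit the overall column promised in 9.5.3.

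The numerical effect depends on how many patients enter with graded values and how those patients spread over doses, which the documents do not give. The MTD decision is not affected, because Section 9.5.1 bases it on DLT counts. The conclusion assumes that treatment group means dose group, that the unsupplied SAP text does not add the missing table, and that some admitted baseline abnormalities carry a CTCAE grade (the grading scale is not reproduced in the documents). The point should be corrected before database lock.

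**What to change.** For the laboratory tables:

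- Produce Tables 14.3-2.1.5, 14.3-2.2.5 and 14.3-2.5.5 by dose group plus All Doses, in line with the general rule in Protocol 9.5 for categorical safety endpoints.
- Add one row per parameter, by dose, for an increase of at least one grade from baseline.
- Keep patients without a baseline grade in the Missing row and count any Grade 1 or higher value as emergent, as in 9.5.4. Amend the footnote and denominator to match.
- Define the on-treatment window and reconcile it with the last-dose window of 9.5.4, stating whether values after the final Day 5 dose count.

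For the adverse-event tables, display in 14.3-1.2 to 14.3-1.8 the total that is already used for sorting.

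The cost is shell edits, some programming and longer tables. No new data are needed. If the SAP text outside the shells already specifies a by-dose emergent laboratory table, add its shell and its entry in the table list.
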